9.3 Secondary study parameter(s)

Continuous normally distributed variables will be expressed by their mean and standard deviation or, when not normally distributed, as medians and their interquartile ranges. Categorical variables will be expressed as frequencies and percentages. Differences between groups in continuous variables will be analyzed with Students t-test or if continuous data is not normally distributed, the Mann-Whitney U test will be used. Categorical variables will be compared with the Chi-squared test or Fisher's

exact test, as appropriate. Time-dependent data will be expressed with Kaplan-Meier curves.

9.4 Cost-effectiveness analysis

Alongside the proposed RCT a prospective economic study will be performed. The economic evaluation primarily focuses on the possible gained benefits of ventilation with the lowest possible PEEP versus ventilation with the PEEP level currently practiced and the associated healthcare costs within 28 days (the primary outcome of the RCT).

Incremental Cost Effectiveness Ratios (ICER) will be calculated by extra costs per TISS/NAS point, a valuable score reflecting workload and resource utilization in daily ICU practice.^{49,50} Cost calculations will be based on actual performance and resource use in routine ICU care during the study follow-up period.

9.4.1 Cost-analysis and time horizon of the analysis

Cost categories and overall costs will be compared between both ventilation strategies and where relevant, differences will be calculated, inclusive of 95% confidence intervals. Additional costs as a result of comorbid conditions will be excluded. The economic evaluation will be set-up as a cost-effectiveness analysis (CEA). The time horizon will be limited to the short-term follow-up (i.e., 28-days, 90-days). With this time horizon no discounting of costs and effects will be performed.

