7.1.3 Other study parameters

Health care related costs will be estimated from the health systems perspective over the time horizon of this trial. Costs include costs of ventilation, costs of stay in ICU,

costs of stay in hospital, costs of use of inotropes and vasopressors, costs of use of sedatives, costs of use of tracheostomies, costs of ventilator-associated pneumonia. Costs will be determined for both PEEP arms during the 28 days follow up period after initial ICU admission. These are used to calculate incremental cost per mechanical ventilation-day avoided.

Lung ultrasound (LUS): within 12 hours after enrolment in the RELAX study, after 24-48 hours after enrolment and within 24 hours after extubation, a LUS will be performed to monitor changes in lung aeration. This is only done in patients admitted to the AMC (see appendix IV: RELAXLUS).

Cardiac ultrasound (ECHO): 24-48 hours after enrolment in the RELAX study, a transthoracic echocardiography (TTE) will be performed to assess the cardiac function. This is only done in a total of 68 patients admitted to the AMC (see appendix V: RELAXECHO).

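### The cost analysis excludes comorbidity-related costs under an undefined rule that conflicts with comparing overall costs as actually incurred, and its 28-day and 90-day horizons are not reconciled

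*Protocol*

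**What the plan says.** **What is costed.** Protocol 7.1.3 says "Costs include costs of ventilation, costs of stay in ICU", and continues with "costs of stay in hospital, costs of use of inotropes and vasopressors, costs of use of sedatives" and further items. Section 9.4 adds: "Cost calculations will be based on actual performance and resource use in routine ICU care during the study follow-up period". Section 9.4.2 covers procedures and units associated with the ventilation strategies, and its examples include vasopressors, sedatives, ventilator days, and ICU and hospital days. Section 9.4.3 defines cost as volume used times unit price.

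**What is compared and removed.** Section 9.4.1 says "Cost categories and overall costs will be compared between both ventilation strategies", and shortly afterwards "Additional costs as a result of comorbid conditions will be excluded".

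**Time horizon.** Section 7.1.3 says "Costs will be determined for both PEEP arms during the 28 days follow up period after initial ICU admission". Section 9.4 also refers to costs within 28 days. Section 9.4.1 describes a short-term horizon and names both 28 and 90 days.

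**Blinding.** Section 7.2 says that blinding is not possible because of the nature of the treatment. Nothing is said about who would attribute costs to comorbidity.

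**The concern.** A between-arm cost difference is protected by randomisation when every cost in the chosen categories counts in both arms. Once some costs are removed because of their presumed cause, the comparison also depends on who judged the cause and how. Critically ill patients often have other disease, and a day in ICU is not recorded as belonging to ventilation or to another condition. If the rule is applied to such days or to drug use, it calls for a judgement made after randomisation, in a trial where treatment is known.

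At stake are the cost comparison, the cost-effectiveness ratio (9.4.4) and the national budget impact analysis (9.5), which builds on the ICU cost reduction estimated in the trial. A horizon stated in two ways adds a second problem: the main economic result could be reported over either period, although most of the listed data serve only the shorter one.

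**Working it through.** The economic sections state no unit cost, expected cost difference or power, so there is no planned figure to reproduce. The check sets the passages side by side and then does simple arithmetic.

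**1. Is there a rule for the exclusion?**

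| Needed to apply it | Where it would stand | Found |
|---|---|---|
| Definition of a comorbidity-related cost | 9.4.1 to 9.4.3 | None |
| Attribution of a day, drug or procedure | 7.4, 7.4.1 | No such field. Severity scores and reason for admission are collected, but they do not assign costs |
| Assessor masked to arm | 7.2, 9.4.1 | Not mentioned |
| The same carve-out in the cost lists | 7.1.3, 9.4, 9.4.2, 9.4.3 | None |

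**2. What the exclusion does to the comparison.** Let *C* be the true mean cost in an arm and *p* the share excluded. The retained cost is *C*(1 − *p*). With equal true costs in arms A and B:

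spurious relative difference = (1 − *p*_B)/(1 − *p*_A) − 1.

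The protocol gives no value for *p*. The following values are assumptions, with *p*_A = 0.20:

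| *p*_B | Gap (points) | Retained, B vs A | Spurious difference |
|---|---|---|---|
| 0.18 | 2 | 0.82 / 0.80 = 1.025 | 2.5% |
| 0.15 | 5 | 0.85 / 0.80 = 1.0625 | about 6% |
| 0.10 | 10 | 0.90 / 0.80 = 1.125 | 12.5% |

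The arm with less excluded looks dearer. Swapping the arms reverses the direction.

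Even attribution is not neutral. With *p* = 0.20 in both arms, a true difference *D* is shown as (1 − 0.20)*D* = 0.80*D*.

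The distortion enters the numerator of the cost-effectiveness ratio. No matching exclusion is stated for its denominator, TISS/NAS.

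**3. Does data collection support both horizons?**

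- The daily items in 7.4 stop at day 28, or at ICU discharge if earlier. They therefore cover at most 28 of 90 days. The remaining 90 − 28 = 62 days (62/90 = 69%) have none of these daily items.
- At day 90, 7.4 lists location and life status only.
- TISS/NAS, the effect measure in 9.4 and 9.4.4, is listed in 7.4.1 until liberation from the ventilator. For a patient off the ventilator, no further effect data are listed to set against costs up to day 90.
- Section 9.4.2 also draws resource use from the hospital information system, databases, financial reports and patient files, with no end date. Hospital length of stay (7.1.2) has no stated day-28 cap.

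Hospital costs to day 90 are therefore obtainable in principle. What is missing is a listed resource item for days 29 to 90, a named source for care outside hospital, and an effect measure that runs over the same period.

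**The case against.** The strongest reply is that the sentence in 9.4.1 may mean only separate items unrelated to ventilation, much as 9.4.2 leaves out protocol-driven costs. ICU days, hospital days, vasopressors and sedatives are expressly included, so nothing says that days are to be split. This reading is possible, and the protocol does not rule it out. It does not settle the matter: the sentence follows a promise to compare overall costs and has no definition, so a second analyst could apply it to days or drugs. If the narrow reading is meant, deleting the sentence should lose little.

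It may also be said that costing detail belongs in an analysis plan, which is not at hand. That would excuse silence, but here the protocol states a rule that conflicts with its own cost definitions.

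Several stronger readings are tempting and are not supported:

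- *No resource data exist after day 28, so a 90-day total would have to be invented.* The sources in 9.4.2 have no end date, and hospital stay is not capped.
- *Attribution will be unblinded.* Section 7.2 concerns treatment. The protocol is silent on cost attribution, so the risk is an inference from the open design.
- *The exclusion removes treatment harm because harms act through existing disease.* The protocol links haemodynamic compromise to atelectasis or overdistension (5.2, 5.3), not to comorbidity.
- *Pneumonia is counted twice.* Section 7.1.3 lists "costs of ventilator-associated pneumonia" beside ICU and hospital stay, but does not say that it includes those days. It may equally mean diagnostics and drugs.

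Finally, costs are an other study parameter (7.1.3). The primary endpoint and the non-inferiority conclusion are untouched, which limits the weight of the point.

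**Conclusion.** The concern holds in two parts. First, the comorbidity exclusion is undefined and conflicts with comparing overall costs based on actual resource use. In an open trial it leaves room for judgement after randomisation that could bias the cost difference, the cost-effectiveness ratio and the budget impact. The direction is unknown. The 2.5% to 12.5% range is an illustration that assumes equal true costs, 20% excluded in one arm, and 2 to 10 points less in the other; it is not an estimate for this trial. Second, the 28-day period in 7.1.3 and 9.4 does not agree with the two horizons in 9.4.1, and the listed daily items and the TISS/NAS effect measure fit the shorter one. Both should be corrected before the economic analysis. Neither affects the clinical conclusions.

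**What to change.** - **Section 9.4.1, exclusion:** delete the sentence. State that all costs in the listed categories count in both arms regardless of cause. If an analysis without comorbidity-related costs is still wanted, make it a sensitivity analysis with a written attribution rule and an assessor masked to arm.
- **Sections 7.1.3, 9.4 and 9.4.1, horizon:** name 28 days as the primary horizon throughout. Keep 90 days only as a secondary analysis of costs, drawn from the hospital records named in 9.4.2, and state that care outside hospital is not covered unless a source is added.

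The cost is a change of wording and no new data collection. Counting all costs is less work than attributing them. The price is somewhat more variable costs, and hence somewhat wider intervals for the cost difference. The 90-day analysis would need the extraction window from hospital records to be set to day 90.

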9.4.2 Measurements

The prospective cost evaluation will primarily focus on health care utilization (direct medical costs). The direct medical costs include the costs of all procedures and units associated with the ventilation strategies (e.g. fluids, vasopressors, sedatives, and ventilator days, ICU and hospital days). Health care utilization will be extracted from the hospital information system, hospital databases (e.g., the National Intensive Care Evaluation (NICE) score, see www.stichting-nice.nl), case record forms (CRFs), financial reports, and patient files. Health service resource use and costs of both ventilation strategies will be measured from a health service and (if relevant) societal perspective. Protocol driven costs will be excluded.

9.4.3 Unit costs

Costs are defined as the volumes of used resources multiplied by calculated unit prices. For the evaluation of health care utilization standard prices published in the

current Dutch costing guidelines and market prices will be used. Standard guideline prices will be used (e.g., diagnostic interventions, hospital admissions).⁵¹

9.4.4. Statistical analysis of Cost-effectiveness

As most volumes of resource use follow a skewed distribution, differences between the two ventilation strategies will be statistically evaluated with bias-corrected bootstrap analysis.⁵² Incremental cost-effectiveness ratio will be calculated with the registered TISS/NAS-score as performance and effect parameter. The economic analysis will be expanded with a scenario-analysis to extrapolate the consequence of implementation and actual performance of the ventilation strategy with 'restricted PEEP' in the target population. The validity of the developed scenarios will be explored in a sensitivity analysis changing cost estimates and probabilities.

9.5 Budget Impact Analysis (BIA)

A budget impact analysis (BIA) will be designed and executed according to the ISPOR guidelines.^{53,54} The BIA will evaluate the nationwide economic/financial consequences of the adoption of treating non-ARDS patients at the ICU with ventilation with the lowest possible PEEP level or ventilation with the currently practiced PEEP level in the future. The analysis will be based on the decrease in ICU costs (e.g. ventilator-free days and alive at day 28) as estimated during the study. Registered data will be used, reflecting the size and characteristics of the eligible population in the Netherlands, the current and the new treatment mix, the effectiveness of ventilation with the currently practiced PEEP level and resource use and costs for the applied strategies and related side-effects. The BIA will be conducted from the perspective of the health care providers. When relevant, budget impact analysis is generated as a series of scenario analysis.

Additional sensitivity analysis will be performed on the price of the intervention and the diffusion rate from the hospital perspective.

10. ETHICAL CONSIDERATIONS

10.1 Regulation statement

This trial will be conducted according to the principles of the Declaration of Helsinki as stated in the current version of Fortaleza, Brazil, 2013 and in accordance with the Medical Research Involving Human Subjects Act (WMO).

10.2 Recruitment and consent

10.2.1 Deferred consent

For this trial we ask for deferred consent and we appeal to the emergency procedure for consent in medical research as stated in article 6, paragraph 4 of the WMO, as in a presently running trial of ventilation in a similar patient cohort, the 'protective ventilation in patients not fulfilling the consensus definition for moderate or severe ARDS at start of ventilation – PReVENT, a randomized controlled trial (METC 2014_075)⁵⁸, for reasons as explained below.

In patients admitted for ventilatory support to the ICU mechanical ventilation is needed urgently – consequently, mechanical ventilation starts right at ICU admission, or very short thereafter. The injurious effects of ventilation, however, could harm the lungs within hours and as such affect patient outcomes (see **Text box 3 – Ventilation has the potential to harm the lungs – even after a short period of ventilation**). For this reason, we consider it of utmost importance to set the ventilator according to the strategies of interest as soon as possible (i.e., within 1 hour after ICU admission, if ventilation started before admission), or within 1 hour after intubation and start of ventilation, if ventilation started after admission) – not doing so would largely reduce validity of this trial.

Patients admitted for ventilatory support to the ICU are, without exception, incompetent to give informed consent. Persons who may take the role of legal representative in accordance with the WGBO are: a predefined representative, husband or wife, registered partner or other life partner, a parent or child, brother or sister, and incidentally a curator appointed the judge. However, obtaining informed consent from a legal representative in this situation usually takes much time, even by an experienced research team (see **Textbox 4 – Experiences with deferred consent in critically ill patients**). Reasons include the absence of a legal representative at time of intubation and start of ventilation, and early after admission to the ICU the legal

representatives are far more concerned about the wellbeing of the patient than participation in a trial.^{55,56}

For these reasons, we opt for using deferred consent, where informed consent from a legal representative must be obtained as soon as possible, but always within 48 hours after randomization. If informed consent is not obtained, or if a legal representative denies participation within the time window of 48 hours, the patient is excluded and data will no longer be used. Thenceforth the patient is ventilated according to the policy of the attending physician.

Textbox 3 - Ventilation has the potential to harm the lungs – even after a short period of ventilation

Ventilation can harm the lungs, even after a short period of ventilation. If a patient, in the proposed trial, is already ventilated for several hours, injurious effects of ventilation could already be in place, largely reducing validity of the trial outcomes. From experimental animal studies we know that mechanical ventilation can cause effects within hours of ventilation with a high PEEP level.⁵⁷ These findings are in line with results from clinical studies, showing ventilator-related effects after relative short periods of ventilation, e.g. after ventilation during general anesthesia for surgery.⁵⁸ A recent randomized controlled trial of patients undergoing cardiac surgery with hypoxemia, comparing a ventilation strategy including a PEEP level of 8 cm H₂O with a ventilation strategy with a PEEP level of 13 cm H₂O, showed an important effect of mechanical ventilation on the incidence of postoperative pulmonary complications.⁵⁹

Textbox 4 – Experiences with deferred consent in critically ill patients

Most critically ill patients who need ventilation cannot be approached for informed consent for a study at ICU admission. Indeed, those patients are usually in severe respiratory distress, sedated or in coma. A prospective observational study on study recruitment practices in critically ill patients performed by a respected and experienced research group in Canada showed that the time from recognizing study eligibility to obtaining informed consent by a legal representative was as high as 12 hours, even while time from recognition to the first contact with a legal representative was as short as 2 hours.⁵⁵

The experience of ICU patients enrolled under deferred consent is mainly positive. To investigate contentment of patients that were included using deferred consent, a questionnaire was designed for – and distributed under the participants of the large NICE–SUGAR trial⁵⁶, a trial compared a strict blood glucose control strategy with one that accepts higher blood glucose levels.⁵⁷ Of the responders (79% of all participants), a large majority (96%) said to have granted consent if they would have been asked. A large majority (93%) mentioned they were happy with the decision made by the representative at the moment they were incapable of giving informed consent.⁵⁷

This is in line with our personal experience from the PReVENT trial (METC 2014_075),⁵⁸ a currently ongoing RCT in ventilated ICU patients without ARDS in The Netherlands, a study that compares two other ventilation strategies. From the PReVENT study we learned that it is very well possible to inform legal representatives about the trial within 24 hours. However due to longer travel distances for some of the legal representatives, obtaining written informed consent was sometimes not possible within the 24 hours: in as many as 19 out of 174 patients (11%) this was a reason for exclusion of the patient. Interestingly, informed consent could have been obtained within 48 hours in all these cases.

10.2.2 Ethical aspects

We can underpin the idea of ‘clinical equipoise’.⁶⁰ Ventilation strategies with lower PEEP levels (sometimes even no PEEP) and higher PEEP levels have been used over the last decades in patients without ARDS, and we actually do not know what the best PEEP level in these patients is. A recent observational study in ventilation practice in

ICU patients shows that a median PEEP level of 8 cm H₂O is used in patients without ARDS in the Netherlands, and a medium level of 6 cm H₂O is used in the European cohort.³³

10.2.3 No deferred consent in patients who die before obtaining informed consent

In case a patient dies before informed consent could be obtained from the legal representative, we propose to use the data and inform the legal representative about the research without obtaining informed consent. This is in line with the advice from Jansen and colleagues regarding ethical validity and practical feasibility of deferred proxy consent in emergency critical care research and in line with the advice of the Central Committee on Research Involving Humans (CCMO, the Dutch national Ethics Committee) in these circumstances in the early lactate-directed therapy in the ICU.^{56,61}

The CCMO judged that the situation when a patient dies before consent could be obtained is comparable with the situation in which the research project has already finished at the time deferred consent can be obtained. They concluded that the legal representative should be notified about the study, but that seeking consent was not useful anymore due to the lack of consequences. The representation of the patient by a legal representative ends when the patient dies. In the Dutch law, the consent of the patient or his/her relative primarily relates to the participation in the study and not to using the data collected in the study.⁵⁶

10.2.4 Conclusion deferred consent

Critically ill patients in need of ventilation are, without exception, incapable to give informed consent at the moment of ICU admission. Obtaining informed consent from a legal representative takes too much time to allow timely start of the ventilation strategies to be compared in this trial. Timely start is essential due to the risk of the injurious effects on the lungs even after a short period of ventilation not following protocol and thereby reducing the validity of the trial. Both ventilation strategies to be compared in this trial have been used in the last decades, and we do not know what the best PEEP level is.

10.3 Benefits and risks assessment, group relatedness

Burden and risks of the ventilation strategies are uncertain. Ventilation with the lowest possible PEEP level could increase the risk of atelectasis and also the risk of potentially dangerous hypoxemia. Ventilation with the PEEP level currently practiced could increase the amount of overdistended lung tissue and increase hemodynamic compromise. Both ventilation strategies are currently used; there is no additional risk for patients enrolled in this study compared to current practice.

We specifically chose not to exclude incompetent patients for two reasons. First, critically ill patients needing mechanical ventilation should be considered incompetent due to their needs for continuous sedation. Second, the strategies to be compared in this study are to be used in critically ill, intubated and ventilated patients. These conditions are not present in patients who are not suffering from a critical disease. We therefore consider it impossible not to include these patients in a study comparing strategies for mechanical ventilation.

